# **3.8.3.** Selection of Data in the Event of Multiple Records in an Analysis Visit Window

Depending on the statistical analysis method, single values may be required for each analysis window. For example, change from baseline by visit usually requires a single value, whereas a time-to-event analysis would not require 1 value per analysis window.

If multiple, valid nonmissing, continuous measurements exist in an analysis window, records will be chosen based on the following rules if a single value is needed:

• In general, the baseline value will be the last nonmissing value on or prior to the first dosing date of study drug, unless specified differently. If multiple measurements occur on the same day, the last nonmissing value prior to the time of first dosing of study drug will be

considered as the baseline value (ie, for Covance laboratory values). For measurements taken on the same date with visit names of screening and baseline (ie, for vital signs and ECGs), the baseline visit value will be utilized if available. If multiple measurements occur at the same time, the average of these measurements (for continuous data) will be considered the baseline value.

- For postbaseline visits:
  - The record closest to the nominal day (nominal day for Week  $X = (X \times 7)$  day) for that visit will be selected.
  - If there are 2 records that are equidistant from the nominal day, the later record will be selected.
  - If there is more than 1 record on the selected day, the average will be taken, unless otherwise specified.

If multiple, valid nonmissing, categorical measurements exist in an analysis window, records will be chosen based on the following rules if a single value is needed:

- For baseline, the last available record on or prior to the date of the first dose of study drug will be selected. If there are multiple records with the same time or no time recorded on the same day, the value with the lowest severity will be selected (eg, normal will be selected over abnormal for safety electrocardiogram [ECG] findings).
- For postbaseline visits, if there are multiple records with the same time or no time recorded on the same day, the value with the worst severity within the window will be selected (eg, abnormal will be selected over normal for safety ECG findings).

# 4. SUBJECT DISPOSITION

#### 4.1. Subjects Randomized and Treated and Disposition

A summary of subjects randomized and treated will be provided by treatment group and overall for each investigator within a country. The summary will present the number and percentage of subjects in the Safety Analysis Set.

A similar table will be provided by treatment group and randomization stratum. Subjects with a discrepancy in the MELD stratum (< 25 and  $\ge$  25) assignment in IWRS and the stratum assigned based on the screening clinical database-calculated MELD score will use the stratum assignment from the clinical database. Covance test results were used to calculate MELD scores at the screening visit for Subject IDs PPD and PPD (enrolled under protocol Amendment 1); and local laboratory tests results were used to calculate screening MELD scores for all other subjects. Subject ID PPD enrolled under Amendment 1 but used local lab results to assess entry criteria (this was a protocol violation). A listing of subjects with discrepancies in stratification assignment between IWRS and the clinical database at the time of data finalization will be provided.

The randomization schedule used for the study will be provided as a listing.

A summary of subject disposition will be provided by treatment group and overall. Study drug completion will be summarized separately for each of the 2 study drugs in the regimen. This summary will present the number of subjects screened (overall), the number of subjects randomized, and the number of subjects in each of the categories listed below.

- Safety Analysis Set / mITT (ie, randomized and treated)
- FAS (ie, randomized and treated with biopsy-proven severe AH)
- PK Analysis Set
- PK Substudy Analysis Set
- Completed Selonsertib/Placebo
- Did not complete Selonsertib/Placebo with reasons for premature discontinuation of Selonsertib/Placebo
- Completed Prednisolone
- Did not complete Prednisolone with reasons for premature discontinuation of Prednisolone
- Continuing study (if applicable)

- Completed study
- Did not complete the study with reasons for premature discontinuation of study

For the status of study drug completion (for each of the 2 drugs) and study completion and reasons for premature discontinuation, the number and percentage of subjects in each category will be provided. The denominator for the percentage calculation will be the total number of subjects in the Safety Analysis Set.

The following by-subject listings will be provided by subject identification (ID) number in ascending order to support the above summary tables:

- Subject disposition
- Reasons for screen failure (will be provided by screening ID number in ascending order) for subjects screened but not randomized to study drug
- Lot number and carton (prednisolone) or bottle (selonsertib/placebo) ID

#### 4.2. Extent of Study Drug Exposure and Adherence

Extent of exposure to each of the individual study drugs will be examined by assessing the total duration and the level of adherence to each of the study drugs. The percentage of subjects with  $\geq 80\%$  adherence to both drugs in the regimen will be presented.

#### 4.2.1. Duration of Exposure to Study Drug

Total duration of exposure for each individual study drug will be defined as last dosing date of individual study drug minus first dosing date of individual study drug plus 1, regardless of any temporary interruptions in study drug administration, and will be expressed in days. Days on study regimen will be the number of days that the subject was on both drugs simultaneously (ie, minimum of end dates for each of the drugs minus the start date of selonsertib/placebo plus 1). If the last study drug dosing date is missing for an individual study drug, the latest of all study drug end dates for that study drug, clinical visit date, laboratory sample collection date, or vital signs assessment date that occurred during the on-treatment period will be used. For subjects with only the month and year of last dose date, the last dose date will be set to the last day of the month (eg, Subject ID PPD

The total duration of exposure to each individual study drug and for taking both study drugs in the regimen will be summarized using descriptive statistics and using the number (ie, cumulative counts) and percentage of subjects exposed through the following time periods: Baseline (Day 1), Week 1 (Day 7), Week 2 (Day 14), Week 3 (Day 21), and Week 4 (Day 28). A 3 day window (ie,  $\geq$  25 days) will be used for the Week 4 category. Summaries will be provided by treatment group for the Safety Analysis Set.

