- UTI: American Urological Association Adult UTI Guidelines (2016) (https://www.auanet.org/education/adult-uti.cfm). The minimum recommended duration of antibiotic treatment is 5 days for uncomplicated UTI, 7 days for uncomplicated UTI in patients with diabetes, and 14 days for complicated UTI.
- Other infections: Investigator's discretion.

In subjects with documented infection, interruption of prednisolone should be considered at the discretion of the investigator (see Section 7.5: Toxicity Management). GS-4997/placebo does not require dose modification in subjects with infection.

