7.5. Toxicity Management

Treatment-emergent toxicities will be noted by the Investigator and brought to the attention of the Medical Monitor. Whether or not considered treatment-related, all subjects experiencing AEs must be monitored periodically until symptoms subside, any abnormal laboratory values have resolved or returned to baseline levels or they are considered irreversible, or until there is a satisfactory explanation for the changes observed.

Administration of all study drugs may be discontinued due to a clinical or laboratory adverse event. Subjects are allowed to take one study drug and not the other.

Prednisolone may be dose-reduced or interrupted at the discretion of the investigator (e.g. due to new-onset, severe sepsis or diabetes mellitus that cannot adequately be controlled). Prednisolone should be discontinued in subjects with a Lille Score ≥ 0.56 at Day 7 (null responders); these subjects may continue GS-4997/placebo treatment. Except in Lille Score null responders, restarting prednisolone may be considered if the reason for interruption has resolved or become adequately controlled in the opinion of the investigator within 7 days of prednisolone interruption. Any decision to restart prednisolone must be reviewed with the Medical Monitor.

There is no option for GS-4997/placebo dose reduction, but GS-4997/placebo may be interrupted due to drug-related toxicity (see below). If GS-4997/placebo is interrupted, it may be restarted on

a case by case basis if the reason for interruption has resolved or become adequately controlled in the opinion of the investigator within 7 days of GS-4997/placebo interruption. Any decision to discontinue or restart GS-4997/placebo must be reviewed with the Medical Monitor.

Subjects who meet any of the following criteria must stop GS-4997/placebo

- Laboratory Criteria (based on central laboratory data):
 - Total bilirubin > 3x Baseline/Day 1 or nadir (confirmed by immediate repeat testing)
 - ALT and/or AST > 5x Baseline/Day 1 (confirmed by immediate repeat testing), unless the elevation is thought by the Principal Investigator to be secondary to an etiology other than GS-4997-related, drug-induced liver injury (e.g. infection).

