#### 3.8. Analysis Visit Windows

#### **3.8.1. Definition of Study Day**

Study day will be calculated from the date of first dose of selonsertib/placebo (SEL/PLA) study drug as follows:

- For postdose study days: Assessment Date First Dose Date SEL/PLA + 1
- For days prior to the first dose: Assessment Date First Dosing Date SEL/PLA

Therefore, study day 1 is the day of first dose of SEL/PLA study drug administration.

In the event that SEL/PLA and prednisolone (PRED) study drug were not started on the same date, the date of first dose of SEL/PLA will be used as the date of first dose of study drug since subjects are allowed (per protocol Amendment 2) to take "pre-doses" of commercial prednisolone for up to 3 days prior to starting study drug.

The last dosing date for an individual study drug (ie, SEL/PLA or PRED) will be the end date recorded for that study drug on the study drug administration eCRF where the "subject permanently discontinued" flag is marked 'Yes'. The last dosing date for any study drug will be the maximum of the last dosing dates for SEL/PLA and PRED.

If the last dosing date of SEL/PLA or PRED is missing or incomplete, the date of last dose will be estimated using the maximum of nonmissing study drug start or stop dates (for the study drug of interest), visit dates, and laboratory collection dates (posttreatment visits and unscheduled visits are not included).

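### The formula for days on study regimen in SAP 4.2.1 counts days on which either drug was temporarily interrupted, so it overstates time on both drugs for subjects with interruptions

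*SAP*

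**What the plan says.** SAP 4.2.1 defines two kinds of exposure.

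- **Each drug separately:** last dosing date minus first dosing date plus 1, "regardless of any temporary interruptions in study drug administration".
- **The regimen:** "number of days that the subject was on both drugs simultaneously (ie, minimum of end dates for each of the drugs minus the start date"; the date meant is when selonsertib/placebo began, and 1 is then added.

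The statement about interruptions belongs to the single-drug durations. The regimen sentence has its own definition and says nothing about interruptions. Both quantities are summarised by arm in the Safety Analysis Set (Table 15.11.1), as descriptive statistics and as cumulative counts through Weeks 1 to 4. The Week 4 category requires at least 25 days.

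The protocol foresees one drug being stopped while the other continues. Section 7.5 states "Subjects are allowed to take one study drug and not the other" and "Prednisolone may be dose-reduced or interrupted at the discretion of the investigator". It also allows selonsertib/placebo to be interrupted for drug-related toxicity. For both drugs, restart may be considered if the cause resolves or is controlled within 7 days. Section 6.9.9 adds: "In subjects with documented infection, interruption of prednisolone should be considered at the discretion of the investigator", while selonsertib/placebo needs no modification for infection. Section 5.3.2 limits prednisolone to 28 days from Day 1, so interrupted days cannot be made up later.

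**The concern.** The definition and the formula agree only when neither drug is interrupted. If one is paused and resumed, the paused days still count as days on both, although the subject was then on one drug or none.

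The primary objective is the safety and tolerability of the combination, and this is the planned summary of how long subjects took it. A reader of Table 15.11.1 would take the regimen rows at face value. The error can only be upward. If interruptions were more frequent in one arm, that arm's combined exposure would be inflated more, and a real difference in time on both drugs would be partly hidden in this table.

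**Working it through.** The plan states no figure for this quantity, so there is nothing to reproduce. The check compares the SAP formula with a direct count of days on which both drugs were taken.

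**Inputs.** Course length of 28 days (SAP 1.2); restart considered within 7 days (Protocol 7.5); Week 4 threshold of 25 days (SAP 4.2.1). The dosing patterns are illustrative assumptions.

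**Formulas.**
- SAP: min(selonsertib/placebo end, prednisolone end) − selonsertib/placebo start + 1.
- Direct count: days in the overlap of the two dosing periods, less days on which at least one drug was interrupted.

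| Pattern | SAP | Direct count | Excess |
|---|---|---|---|
| Both Days 1–28, no interruption | 28 | 28 | 0 |
| Prednisolone begun 3 days before selonsertib/placebo | 28 | 28 | 0 |
| Prednisolone stopped permanently at Day 7 | 7 | 7 | 0 |
| One drug interrupted 3 days | 28 | 25 | 3 (3/25 = 12%) |
| One drug interrupted 7 days, or both on the same 7 days | 28 | 21 | 7 (7/21 = 33%) |
| Each drug interrupted 7 days, at different times | 28 | 14 | 14 (14/14 = 100%) |
| Prednisolone begun 3 days after selonsertib/placebo | 28 | 25 | 3 (3/25 = 12%) |

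**Week 4 category.** With an otherwise full course, 4 to 7 interrupted days leave 24 to 21 days on both drugs. All are below 25, yet the formula gives 28 and counts the subject as exposed through Week 4. Three interrupted days leave 25, so the category is still correct.

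**Group mean.** The documents give no interruption rate. Assume a share *f* of subjects has one 7-day interruption and all others have 28 days. The mean is overstated by 7*f* days against a true mean of 28 − 7*f*:
- *f* = 10%: 0.7 against 27.3 (2.6%)
- *f* = 20%: 1.4 against 26.6 (5.3%)
- *f* = 30%: 2.1 against 25.9 (8.1%)

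**What other outputs show.** Adherence (SAP 4.2.2) is a pill count per drug, and temporary interruption does not reduce the expected count. Seven days off prednisolone leave 21 × 4 = 84 of 112 tablets, or 75%, which falls below the 80% threshold. Five days off leave 23/28 = 82%, which passes. Five days off each drug at different times leave 82% for both drugs, yet only 28 − 10 = 18 days on both, where the formula gives 28.

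**The case against.** The strongest reply is that the regimen row follows the convention openly stated one sentence earlier, first to last dose ignoring interruptions, and that the formula says exactly what is computed. Subtracting interruptions would mix two conventions in one table and change a derivation after the primary analysis was unblinded (SAP 2.3). This stands as a cost. It does not remove the mismatch, because the regimen sentence promises simultaneous use and carries no such qualification.

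Three stronger readings are tempting, and the documents do not support them.

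- **That the selonsertib/placebo start date is itself an error.** SAP 3.8.1 covers different start dates ("In the event that SEL/PLA and prednisolone (PRED) study drug were not started on the same date"), but the only reason it gives is prednisolone taken for up to 3 days beforehand. Selonsertib/placebo is then the later start, and the overlap begins in the right place. The formula would overstate only if study prednisolone began after selonsertib/placebo, which the documents neither plan nor exclude.
- **That adverse event rates are distorted.** SAP 7.1.6 plans numbers and percentages of subjects. Treatment emergence (SAP 7.1.5.1) runs from study drug start to 30 days after permanent discontinuation. Regimen days enter neither.
- **That a less tolerable arm would pass as equally tolerant.** Tables 15.11.5.4 to 15.11.5.6 report events leading to interruption by drug, and adherence and dosing listings are planned as well. These show much of any difference. They do not give days of overlap: the interruption tables count subjects, and adherence can pass 80% for both drugs while overlap is well short of 28 days.

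**Conclusion.** The point holds as a minor inconsistency. For a subject with interruptions, the formula exceeds days on both drugs by exactly the number of days, up to the earlier end date, on which at least one drug was interrupted. That is 28 against 21 for one 7-day interruption, with a wrong Week 4 category. Subjects without interruptions, with prednisolone pre-dosing, or with permanent discontinuation of one drug are counted correctly, so it would be wrong to say that combined exposure is overstated in general.

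The group-level size rests on an assumed interruption rate. The 52% in Protocol 1.1 is the share of corticosteroid-treated patients who developed infections in a cited cohort. It cannot serve as an interruption rate, since Protocol 6.9.9 asks only that interruption be considered. A difference in bias between arms is possible but not shown, because both arms receive prednisolone. The effect is confined to the descriptive regimen rows of Table 15.11.1; no test or adverse event percentage depends on them.

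**What to change.** Either of two changes to SAP 4.2.1 removes the inconsistency.

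1. **Correct the calculation for the regimen rows and their Week 1 to 4 categories.** Use the earlier end date minus the later start date plus 1, less the days in that span on which either drug was recorded as interrupted on the study drug administration eCRF. The later start date is only a safeguard.
2. **Keep the formula, relabel it and add a row.** Call the existing quantity time from selonsertib/placebo start to first permanent discontinuation of either drug, interruptions ignored. Report the net overlap from option 1 beside it.

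The single-drug durations stay as they are. SAP 3.8.1 takes the last dosing date from the eCRF record flagged as permanent discontinuation, which implies several records per drug. Interrupted days should therefore be derivable with minor programming, though the eCRF itself is not in the documents.

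The cost is a slightly shorter combined exposure figure, and a regimen row that follows a different convention from the single-drug rows and from the primary-analysis table. A footnote should say so. Option 2 keeps a row comparable with the primary analysis.

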# 4.2.2. Adherence to Study Drug

The level of protocol defined adherence to each of the 2 study drugs will be determined by the total amount of study drug administered relative to the total amount of study drug expected to be administered based on what is specified in the protocol.

The level of adherence will be expressed as a percentage using the following formula:

On-Treatment Adherence (%) = 
$$\left(\frac{\text{Total Amount of Study Drug Administered}}{\text{Study Drug Expected to be Administered on Treatment}}\right) \times 100$$

Total amount of study drug administered will be the total number of pills dispensed minus the total number of pills returned. If a bottle (selonsertib/placebo) or carton (prednisolone) of study drug is not returned, the subject will be assumed to have not taken the pills.

Subjects are expected to take 28 tablets containing SEL (18 mg)/PLA and 112 tablets containing 10 mg of PRED; unless the subject is prematurely terminated from study drug due to death, lack of efficacy (meeting Lille score criteria [ie,  $\geq 0.56$  at Week 1 for prednisolone; or > 0.85 at Weeks 1, 2, 3, or 4 for both study drugs]), or does not have biopsy-proven severe AH on biopsy (ie, variable SDRGREAS\_STD equal to 'PW', 'PV', 'LE, or 'DT' on the study drug completion eCRF for an individual study drug and subject). Subjects who were transplanted while on study drug (eg, Subject ID PPD should also only have adherence calculated to their last dose date of study drug. Note that no subjects in the study had positive results for HBsAg, HCV RNA or HIV-1/HIV-2 per central laboratory assessment which was also a criteria for calculating adherence to last dose date. Subjects who do not complete individual study drug completion form, will have adherence for that study drug calculated to last dose date of individual study drug.

In addition, subjects meeting individual SEL/PLA subject stopping criteria for the study (eg, Grade 3 or higher treatment-emergent AE that is considered to be related to study drug and results in premature discontinuation of SEL/PLA, confirmed ALT or AST > 5 x baseline, confirmed total bilirubin > 3 x baseline or nadir, or ALT or AST > 500 U/L) who prematurely discontinued SEL/PLA will have adherence for SEL/PLA calculated to their last dose date of SEL/PLA (ie, Subject ID PPD for confirmed ALT > 5 x baseline).

Descriptive statistics for the level of on-treatment adherence to each of the 2 study drugs will be provided by treatment group for the Safety Analysis Set. The number (%) of subjects who are  $\geq 80\%$  compliant to each of the 2 study drugs will be presented.

A separate by-subject listing of study drug administration and study drug accountability will be provided by subject ID number (in ascending order) and visit (in chronological order).

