Eligible subjects will be randomized to one of the two treatment groups. Prior to initial dosing, required Baseline/Day 1 assessments will be performed and will include vital signs, PE, HE, ascites, HRS and infection assessment, laboratory assessments, pregnancy tests (for females of child-bearing potential), and review of adverse events, concomitant medication, CLDQ questionnaire and alcohol consumption.

While on study, subjects will undergo the following procedures and laboratory assessments:

- CLDQ questionnaire at Baseline/Day 1, Weeks 4 and 24
- Sparse PK Sampling at Baseline/Day 1 and at Weeks 1, 2 and 4
- Blood for Biomarkers at Screening, Baseline/Day 1, and at Weeks 1, 2, 4, 8, 12 and 24
- Urine collection for Biomarkers at Baseline/Day 1, and at Weeks 4 and 24
- ELFTM Test and LOXL2 at Baseline/Day 1 and at Weeks 4, 12 and 24
- FibroScan (if available and in subjects without ascites) at Baseline/Day 1 and at Weeks 4 and 24
- 12-lead ECGs at Screening, Baseline/Day 1, and at Weeks 4 and 8

[figure not shown]
Treatment will be administered for 28 days inclusive of inpatient, and if applicable, outpatient periods.
Up to 60 subjects per arm will be randomized in order to obtain 50 subjects in each arm for the full analysis set (ie, subjects randomized with histologically-proven severe AH who took at least one dose of study drug)
 Treatment Group B: GS-4997 placebo (1 tablet) AND prednisolone 40 mg (4 x 10 mg tablets) administered orally once daily; n=50-60 subjects
• Treatment Group A: GS-4997 18 mg (1 x 18 mg tablet) AND prednisolone 40 mg (4 x 10 mg tablets) both administered orally once daily; n=50-60 subjects
PPD
Intensive PK Sub-study
• Stool collection at Baseline/Day 1 and at Weeks 4 and 24.
 Urine collection at Screening (for drug screen, pregnancy screen, and to rule out infection)
• Hemoglobin A1c at Baseline/Day 1 and at Weeks 12, and 24
 Blood glucose, insulin and lipid profile at Screening, Baseline/Day 1 and at Weeks 4, 12 and 24

Criteria for Evaluation:

Cafatan	Cafate will be avaluated by avamining the insidence of treatment
Safety:	Safety will be evaluated by examining the incidence of treatment emergent adverse events, including serious adverse events, clinical laboratory tests, ECGs, and vital signs.

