5.2.2. Packaging and Labeling

5.2.2.1. GS-4997 18 mg and GS-4997 PTM

GS-4997 18 mg and GS-4997 PTM tablets are packaged in white high density polyethylene (HDPE) bottles. Each bottle contains 30 tablets, silica gel desiccant and polyester packing material. Each bottle is enclosed with a white, continuous-thread, child-resistant polypropylene screw cap with an induction-sealed and aluminum-faced liner.

Study drug to be distributed to centers in the US and other participating countries shall be labeled to meet applicable requirements of the United States Food and Drug Administration (FDA), EU Guideline to Good Manufacturing Practice - Annex 13 (Investigational Medicinal Products), and/or other local regulations.

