- Administer or dispense GS-4997/placebo and prednisolone, and provide subject with dosing instruction on appropriate dosing and administration
- FibroScan (if available and for subjects without ascites).
- 6.3. Treatment Assessments

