Liver Ultrasound		x	2		8				8		3										
Review Concomitant Medications		x	ŝ	X		X		X		X		X	x	x	X	X	X	x	X	X	

GS-4997 Protocol GS-US-416-2124 Gilead Sciences, Inc.

	Screening ^a			Treatment ^b					Post	Treatme	nt			Unscheduled Visit	
		Baseline/	Week 1	Week 2	Week 3	Week 4/ EoT ^t	Week 6	Week 8 ^u	Week 12 ^u	Week 16	Week 20	Week 24 ^u	Follow Up visit ^v		
	-14 days	Day 1			±3 days						±5 days				
Adverse Events	X	Х	Х	X	Х	X	X	Х	X	Х	X	X	X	x	
Sparse PK Sample ^p		Х	Х	X		X ^p									
Stool Collection		Х				X						X			
Randomization ^q		X			2			-				-			
GS-4997 Dispensing		Х													
Prednisolone Dispensing		X	X	E E	X						3				
PPD															
Genomic Sample ^s		Х				-		-					-		
Study Drug Adherence			Х	X	х	X									
FibroScan ^w		X				X						X			
Lille Score ^x			Х	X	Х	X									

a The visit window may be extended under special circumstances with explicit approval of the Medical Monitor. Subjects who fail to meet eligibility criteria due to an abnormal laboratory result may undergo re-testing of the abnormal analyte once during the Screening window. This will be done at the discretion of the investigator and also with prior approval of the Medical Monitor. The following laboratory tests will be collected at Screening for testing at both the local and central laboratories: urine drug screen, hematology, chemistry, and coagulation tests. Eligibility will be based on local laboratory results. For urine drug screen, local laboratory testing done within 10 days of the Screening visit may be used to determine eligibility. For hepatitis B serology, hepatitis C serology, and HIV serology, these tests will be sent to both the local and central laboratory and be the basis for eligibility. A serum pregnancy test will be sent only to the central laboratory at Screening.

b During the hospitalization period, subjects will be evaluated daily with assessments to include a review of adverse events, concomitant medications, study drug adherence, and a symptom-directed PE including assessments for ascites and HE. Findings based on these assessments and laboratory investigations obtained by treating physicians as part of routine care will be assessed by the investigator for triggers that may necessitate further evaluation and/or treatment discontinuation and managed accordingly per Section 7 of the protocol.

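### Counting an unreturned bottle as no pills taken reports 0% GS-4997/placebo adherence for a subject who may have taken every dose; show how many subjects this affects and add an alternative row

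*SAP*

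**What the plan says.** SAP 4.2.2 defines on-treatment adherence, separately for each drug, as the amount administered divided by the amount expected, times 100. For the numerator, "Total amount of study drug administered will be the total number of pills dispensed minus the total number of pills returned". For the denominator, "Subjects are expected to take 28 tablets containing SEL (18 mg)/PLA and 112 tablets containing 10 mg of PRED", with the expected amount cut back to the last dose date for listed reasons such as death, transplant, Lille stopping or a biopsy that does not confirm the disease. Between the two stands the rule at issue: if a bottle or carton "of study drug is not returned, the subject will be assumed to have not taken the pills". The section gives no exception, no missing category and no fallback to dosing dates.

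On supply, Protocol 5.2.2.1 says of GS-4997 and its placebo: "Each bottle contains 30 tablets". In Protocol Appendix 2 the row "GS-4997 Dispensing" carries one mark, at Baseline/Day 1. The visit text agrees. Protocol 6.2.2 has the site "Administer or dispense GS-4997/placebo and prednisolone", while the Week 1 and Week 3 visits (6.3.1, 6.3.3) list prednisolone only.

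Exposure comes from another source. Under SAP 4.2.1, "Total duration of exposure for each individual study drug will be defined as last dosing date of individual study drug minus first dosing date" plus 1, and Protocol 8.8.1 takes exposure from the study drug administration page of the eCRF.

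**The concern.** A container that does not come back tells us nothing about whether its contents were swallowed. The rule turns that absence of information into a definite value, and for a drug supplied in a single container the value is the most extreme one possible. The reported 0% can contradict the trial's own dosing record for the same subject. It is also implausible in the population used: adherence is summarized for the Safety Analysis Set, which requires at least one dose (SAP 3.1.4).

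At stake are the descriptive adherence results: the mean and other summary statistics for GS-4997/placebo, the number at or above 80% for each drug, and the share at or above 80% for both drugs (SAP 4.2). A reader of these tables could take an artefact of bottle return for under-dosing.

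**Working it through.** **Inputs**
- Course: "Treatment will be administered for 28 days inclusive of inpatient" and outpatient periods (Protocol Synopsis), with one GS-4997/placebo tablet and four 10 mg prednisolone tablets a day.
- GS-4997/placebo bottle: 30 tablets (Protocol 5.2.2.1).
- Scheduled GS-4997/placebo dispensings: one (Protocol 6.2.2 and Appendix 2).
- Arm size: 50 to 60 (Protocol 3.2).
- Reporting threshold: 80% (SAP 4.2.2).

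**The plan's own figure.** Expected tablets are 28 × 1 = 28 GS-4997/placebo and 28 × 4 = 112 prednisolone. Both match SAP 4.2.2.

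**One subject who took all 28 doses**
- Bottle returned with 2 tablets left: (30 − 2)/28 = 100%.
- Bottle lost, SAP rule: 0/28 = 0%.
- Bottle lost, formula without the special rule and 0 returned: 30/28 = 107%, or 100% if capped at 28.

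Some convention is therefore needed for lost bottles, because the plain formula also misbehaves, in the other direction. Shortening the denominator does not help: 0 over any expected amount is still 0%. Exposure for this subject under SAP 4.2.1 would be 28 days.

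The threshold is 0.80 × 28 = 22.4, so 23 tablets are needed. A subject at 0% falls below it for GS-4997/placebo, and so also for both drugs jointly.

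**Effect on an arm.** Moving one fully adherent subject from 100% to 0% lowers the arm mean by 100/n points, whatever the other subjects' values, and lowers the share at or above 80% by the same amount. The counts of lost bottles below are illustrative; the documents give none.

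| Lost bottles | Fall, n = 60 | Fall, n = 50 |
|---|---|---|
| 1 | 1.7 points | 2.0 points |
| 3 | 5.0 points | 6.0 points |
| 5 | 8.3 points | 10.0 points |

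**Prednisolone.** It is dispensed at Baseline/Day 1, Week 1 and Week 3, so one lost carton does not give 0%. Carton size is not stated. Assume one carton per dispensing, covering the 7, 14 and 7 days to the next one. A fully adherent subject who loses one would score (112 − 28)/112 = 75%, (112 − 56)/112 = 50%, or 75%. The threshold is 0.80 × 112 = 89.6, so 90 tablets, and all three values fall below it.

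**The case against.** The rule is an explicit, prespecified worst-case convention. It contradicts no other adherence formula in the protocol, and choosing among zero, missing and date-based values for pills nobody can count is a matter of convention. That stands, so this is not an error of arithmetic or an internal contradiction.

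No efficacy or safety analysis uses adherence. No per-protocol set is defined, and the mITT, Full and Safety sets depend on dosing and, for the Full Analysis Set, histology (SAP 3.1.2 to 3.1.4). That also stands, and it limits the point to descriptive tables.

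There are safeguards. All used and unused drug must be returned (Protocol 5.6), accountability and adherence are checked at Weeks 1 to 4, and adherence is reviewed daily in hospital. Exposure is tabulated separately, and by-subject listings of administration and accountability are planned. These make an anomalous subject traceable, but they do not correct the summary percentages.

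That a subject has one bottle is an inference from the dispensing schedule and bottle size; no sentence says so. Protocol 6.6 allows an unscheduled visit solely to refill medication, without naming the drug. A subject given a second bottle would not score 0% from losing one.

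A reader might go further and infer that bottles go missing more often after death or transfer, so that the error tracks outcome or differs between arms. No passage gives return rates by outcome or by arm. A reader might also infer that the zero drives protocol deviations, since SAP 4.3 gives nonadherence as an example. That section says post-entry deviations are documented during routine monitoring; it does not derive them from this percentage.

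**Conclusion.** The point holds as a minor one. As written, SAP 4.2.2 can report 0% GS-4997/placebo adherence for a subject who took every dose, beside 28 days of exposure for that subject. Each such subject costs the arm about 1.7 points (n = 60) or 2.0 points (n = 50) in mean adherence and in the share at or above 80%. This assumes that the lost bottle was the subject's only one and that the subject was fully adherent. A less adherent subject would lower the mean by less. The total effect cannot be stated, because the number of unreturned bottles is not given and could be zero. The documents support no conclusion about bias between arms, and the efficacy and safety results are unaffected.

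**What to change.** Keep the zero rule as the prespecified row and make two additions to the adherence table:

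1. Report, by arm and by drug, the number of subjects with an unreturned bottle or carton.
2. Add a row for mean adherence and for the figures at or above 80% (each drug, and both) in which unreturned containers are handled from the dosing start, stop and interruption dates on the study drug administration eCRF. If those dates are not adequate, set pill-count adherence for these subjects to missing.

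The SAP covers the final analysis, and treatment assignments were already unblinded for the primary analysis (SAP 2.3). The CSR should therefore describe the addition as made after that unblinding. This is a reason to add a row and not replace the rule.

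The cost is a sentence or two of wording and minor programming on data already collected. The drawback is that eCRF dates may overstate intake where missed outpatient doses were not recorded. The two rows should be read together, neither taken as the true value.
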